**Figure 3: Overview of Study Design**

\* For subjects who develop an excess Hb response during the primary efficacy period, the number of tablets of study drug will be decreased (see Section 8.2.4). For these subjects, the number of tablets of vadadustat initiated at the Week 6 visit will be lower than indicated.

The study will include the following periods:

- Eligibility screening period (see Section 9.1 for additional information regarding screening visits and ESA washout period for subjects who were prescribed ESAs at study entry)
  - Up to 4 weeks for subjects who were not prescribed ESAs prior to study entry (Day -28 to Day 0)
  - Up to 6 weeks for subjects who were prescribed epoetin alfa, epoetin beta, and epoetin kapp prior to study entry (Day -42 to Day 0)
  - Up to 8 weeks for subjects who were prescribed darbepoetin alfa prior to study entry (Day -56 to Day 0)
  - Up to 11 weeks for subjects who were prescribed epoetin beta pegol prior to study entry (Day -77 to Day 0)
- Primary efficacy period (6 weeks; Weeks 1 to 6)
- Dose adjustment and maintenance period (10 weeks; Weeks 7 to 16)
- Follow-up period (2 weeks; Weeks 17 and 18)

Subjects will participate in a screening period to determine study eligibility. Subjects who have not recently received ESA therapy will participate in 2 screening visits. Subjects who have recently received ESA therapy and otherwise meet eligibility criteria will be required to washout

from ESA therapy prior to evaluation of screening Hb, and will participate in 3 screening visits (see [Section 7.2](#)).

Eligible subjects will be randomized following the screening period using a central randomization system. Subjects will be randomized 1:1:1 to receive 1, 2, or 4 tablets at their baseline visit (Day 1). Within each tablet-count group, subjects will be randomized 3:1 to receive vadadustat (150, 300, or 600 mg vadadustat) or placebo. See [Section 8.2.2](#) for information regarding the randomization scheme.

Study drug treatment will be administered during a 6-week primary efficacy period. See [Section 8.2.4](#) for information on study drug administration. The primary efficacy period includes fixed-dose treatment to establish a dose-response relationship. However, if Hb level increases rapidly or if the Hb levels exceeds 13 g/dL, the study drug dose can be decreased or interrupted (see [Section 8.2.4](#)).

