## **7.6 Subject Completion and Individual Subject Discontinuation**

### **7.6.1 Subject Completion**

A subject will be considered as having completed the study after completing participation in the Week 18 visit (end of the 2-week follow-up period).

Note: See [Section 7.6.3](#) for subjects who discontinue study drug or withdraw early from the study.

See [Section 10.3.6](#) for information regarding follow-up of unresolved events.

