### **8.2.5 Study Drug Administration during the Dose Adjustment and Maintenance Period (Week 7 to Week16)**

Subjects who complete the primary efficacy period will enter the dose adjustment and maintenance period. Subjects receiving placebo will be switched to vadadustat at the Week 6 visit. Specifically, at the Week 6 visit, sites will collect all unused study drug tablets dispensed during the primary efficacy period. Each subject will then be provided with 1 bottle of vadadustat. Each subject will initially take the same number of tablets of study drug after the Week 6 visit as before the Week 6 visit. For example, subjects taking 2 tablets of study drug (vadadustat or placebo) prior to the Week 6 visit will initially take 2 tablets of vadadustat after the Week 6 visit.

Subsequently, study drug dose will be adjusted to achieve a target Hb of 10.0-12.0 g/dL based on central laboratory Hb results and dose adjustment guidelines described below. Dose adjustments will be based on central laboratory Hb results from study visits at Weeks 6, 8, 10, 12, and 14.

- Do not increase the dose more frequently than once within any given 4-week interval. For example, if a subject's dose was increased based on Hb results from the Week 6 visit and the subject remains below the Hb target, the next opportunity to further increase the dose would be based on Hb results from the Week 10 visit. Decreases in dose can occur more frequently. Avoid frequent dose adjustments.
- If the Hb has not increased by more than 0.5 g/dL above the baseline value after the first 6 weeks of treatment, increase the dose by 1 tablet.
- Increase the dose by 1 tablet every 4 weeks until Hb is above 10.0 g/dL (maximum dose is 4 tablets).
- If the Hb increases rapidly (eg, more than 1 g/dL in any 2-week period), reduce the dose by 1 tablet.
- If the Hb falls below 10.0 g/dL, increase the dose by 1 tablet.
- If the Hb exceeds 12.0 g/dL, reduce the dose by 1 tablet.
- If the Hb exceeds 13.0 g/dL, interrupt study drug until the Hb decreases to 12.5 g/dL or below and then resume dosing with 1 fewer tablet.
- If a dose adjustment is required to maintain Hb at the desired level, the dose adjustment is by 1 tablet.

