4.4.2 Analysis Populations for the Efficacy Analyses

The efficacy summaries and analyses will be based on the **modified intent-to-treat (MITT) population**. The MITT population is defined as all randomized subjects who have received at least 1 dose of study medication and have a pre-treatment Hb average defined as the average of the most recently 2 qualifying screening value and the baseline value, and at least one post-baseline Hb measurement. **The post-baseline Hb measurement will exclude the withdrawal Hb and follow-up Hb measurements for discontinued patients.** In the event that a subject is allocated the incorrect study treatment as per the study randomization list, subjects will be summarized and analyzed ‘as randomized’ i.e. by randomized treatment group.

For the efficacy variables, sensitivity analyses will be performed on the **per-protocol (PP) population** to assess the robustness of the study conclusions to the choice of analysis population. The PP population is defined as the subjects in the MITT population who have completed the study and have efficacy data through Week 6, have a study medication compliance of $\geq 80\%$, and do not have any major protocol deviations expected to significantly affect the primary efficacy endpoint. Subjects with major protocol deviations expected to significantly affect the primary efficacy endpoint will be identified and documented prior to data unblinding.

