4.7.1.5 Preliminary (6-Week) Analysis

After all subject performed assessment of the Week 6 Visit, preliminary analysis will be performed. As the study conduct and final analysis will not be modified by this analysis, no alpha adjustment is proposed. It is expected that this 6-week data will be identical for the preliminary analysis and the final analysis of the complete dataset. Any changes between the preliminary analysis and the final analysis will be documented. The preliminary analysis will be performed by the independent unblinded team. All data through the cutoff date of the last subject randomized who completes week 6 will be analyzed. Blinding of blinded team and investigators will be maintained to prevent potential bias.

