4.7.1.6 Examination of Subgroups

Not Applicable. No subgroup analysis is planned.

4.7.2 Primary Efficacy Variable – Mean Change in Hb from Pre-treatment to the End of the Primary Efficacy Period (Week 6)

The primary variable for the assessment of efficacy is the change from pre-treatment to Week 6 in Hb (g/dL). Change in Hb is defined as the Hb measured at the Week 6 visit

minus the mean pre-treatment Hb. Pre-treatment Hb is defined as the average of 3 Hb values obtained prior to treatment based on 2 qualifying screening Hb values and the Hb value at the baseline visit (Day 1). If screening visit are not performed for some clinical consideration, pre-treatment HB will be calculated as average of available screening HB values and baseline visit without any screening visit imputation. e.g. if only one qualifying screening HB values available in the screening period, then Pre-treatment Hb is calculated as the average of 2 Hb values : only 1 qualifying screening Hb values and the Hb value at the baseline visit (Day 1).

For the primary analysis, the LOCF approach will be used to impute missing data.

4.7.2.1 Summary of actual value and change in Hb at week 6

The primary analysis population for efficacy will be MITT population. The following summary will be provided:

- A summary of actual value of Hb by treatment group at baseline and week 6. A summary of the change (absolute and percent) from pre-treatment average in Hb by treatment group at week 6. 1st and 3rd quartiles (Q1, Q3) as well as the mean, SD, median, minimum, maximum and number of observations will be shown. P values for overall comparison and treated groups vs. placebo on change from pre-treatment will also be presented.
- A waterfall plot for absolute Hb change from pre-treatment average for each treatment group at week 6.

The effect of treatment in terms of the change from pre-treatment to Week 6 in Hb will be analyzed using a one-way analysis of covariance (ANCOVA). The statistical model will assess the main effect of treatment, adjusted for pre-treatment average. Least-squares (LS) means for each treatment and their 95% confidence intervals (CIs) will be presented. Three post-hoc pairwise comparison, i.e., Placebo vs 150 mg, placebo vs 300 mg, and placebo vs 600 mg, will be done. Unadjusted one-way analysis of variance (ANOVA) will be performed for sensitivity.

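### Read literally, the per-protocol set for a Week 6 endpoint requires completion of the Week 18 visit, so it depends on later events and cannot be formed at the preliminary analysis

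*SAP*

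**What the plan says.** Protocol 11.4.2 and SAP 4.4.2 use the same words. PP subjects are MITT subjects "who have completed the study and have efficacy data through Week 6", with at least 80% compliance and no major deviation likely to disturb the primary endpoint. Neither section gives a period for the compliance figure.

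Other sections that bear on this:

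- **Meaning of completion.** Protocol 7.6.1: "A subject will be considered as having completed the study after completing participation in the Week 18 visit".
- **Endpoint.** SAP 4.7.2 sets the primary variable as the change in Hb to Week 6.
- **Switch.** Protocol 8.2.5: "Subjects receiving placebo will be switched to vadadustat at the Week 6 visit". Hb-driven dose adjustment follows for all subjects.
- **Unblinding.** Protocol 8.2.3 keeps all sponsor and CRO staff blinded until the last subject finishes Week 6. SAP 4.4 requires exclusions to be settled before unblinding.
- **Preliminary versus final.** SAP 4.7.1.5: "It is expected that this 6-week data will be identical for the preliminary analysis and the final analysis of the complete dataset". It adds that any differences will be documented.
- **Use of PP.** It is the sensitivity population for the Week 6 analysis (SAP 4.7.2.1). It also serves the Hb summaries beyond Week 6 (4.7.2.2, 4.7.2.3) and the secondary variables, including Week 16 (4.7.3).

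**The concern.** A sensitivity set for a Week 6 endpoint should be defined by what is known at Week 6. The literal rule adds a condition that is met or failed up to 12 weeks later. A subject with a complete, compliant Week 6 record could be dropped from the Week 6 PP analysis because of an event in Weeks 7 to 18. Some of those events are tied to Hb: subjects who start rescue are discontinued (Protocol 8.2.6). For the placebo arm, membership would depend partly on staying in the study while taking active drug.

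There is also a practical problem. When the preliminary analysis is run, study completion is unknown for every subject still in follow-up. A PP set at that point would have to follow some other rule, and its membership could change by the final analysis. At stake is the value of the PP analysis as a robustness check on the Week 6 result.

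**Working it through.** **1. Definition.** The PP rule requires study completion; completion means the Week 18 visit (Protocol 7.6.1). SAP 4.3.1 counts Week 6 completers and Week 18 completers separately, so wording for Week 6 completion was available and is not used in the PP definition.

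**2. Timing.** In Protocol Appendices A and B, Week 6 is Day 43 and Week 18 is Day 127. 127 − 43 = 84 days, or 12 weeks. When the last subject reaches Week 6, that subject's completion status is open for up to 84 more days (nominal days, before visit windows). With completion anchored at Week 6 the gap is 0 days.

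**3. The plan's own power figure.** Protocol 11.2 assumes a difference of 1.35 g/dL, SD 0.9 g/dL, 12 per arm, 10% dropout and two-sided alpha 0.05, and states power above 85%. With n = 12 × 0.90 = 10.8 per arm, power is 93.7% (normal approximation) or 91.2% (noncentral t). The stated bound holds, and this point does not depend on it.

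**4. Precision.** SE = SD × √(2/n). The documents give no exit rate after Week 6, so 10% to 25% is an assumption.

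| n per arm | Derivation | SE at SD 0.9 |
|---|---|---|
| 10.8 | 12 × 0.90 | 0.387 |
| 9.72 | 10.8 × 0.90 | 0.408 |
| 8.1 | 10.8 × 0.75 | 0.447 |

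The relative increase is √(10.8/9.72) = 1.05 to √(10.8/8.1) = 1.15. It does not depend on the SD, so it also holds at the 0.68 g/dL in SAP 4.10.

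The protocol does not say which period its 10% dropout covers. If it covers the whole study and all exits come after Week 6, the comparison is 12 against 10.8 per arm: 0.9 × √(2/12) = 0.367 against 0.387.

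**5. Bias, by illustration only.** Assumptions: Week 6 change is normal with SD 0.9 and means 0 (placebo) and 1.35 (600 mg). The log-odds of exit after Week 6 fall by 1 or 2 per g/dL of Week 6 change. The intercept is set to give the overall exit rate shown across the two arms. The difference among those who remain is:

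| Overall exit | Slope −1 | Slope −2 |
|---|---|---|
| 5% | 1.310 | 1.255 |
| 10% | 1.278 | 1.186 |
| 20% | 1.228 | 1.083 |

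If exit is unrelated to Week 6 Hb, the expected difference stays at 1.35 and only subjects are lost. Other exit patterns would give other results, so neither the size nor the direction is established.

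**The case against.** The best reply is that the phrase can be read so that Week 6 governs both verbs. The rest of the definition points to the Week 6 endpoint, and a Week 18 condition is unworkable at a planned Week 6 analysis, which suggests that Week 6 was meant. This may well be the intent. But neither document says so, and a programmer who applies the defined term would build a different set. The text needs correcting under either reading.

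A reader might go further and infer one of the following. The documents do not support these inferences.

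- **Everyone who leaves after Week 6 is removed.** Protocol 7.6.3 asks early discontinuers to complete the Week 18 assessments, and 7.6.1 ties completion to that visit. Some early leavers could therefore count as completers. This leaves the set undefined rather than known to be smaller.
- **The final PP set cannot be classified blind.** SAP 4.7.1.5 gives the preliminary analysis to an independent unblinded team, and Protocol 8.2.3 hands the study to staff who remain blinded. They can classify the final set. Only the preliminary set is unobtainable under the literal rule.
- **A change between the two analyses breaks the plan.** SAP 4.7.1.5 expects identical 6-week data and provides for documenting differences. It does not list which populations the preliminary analysis covers.
- **Protocol-directed dose reductions count as non-compliance.** No section shows this. What can be said is that the compliance period is not stated.

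It also stands that PP is a sensitivity population and that a later completion rule is more natural for Week 16 summaries.

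**Conclusion.** The point holds as a defect of definition and timing in a sensitivity analysis. On the documents' own definition, the Week 6 PP set depends on up to 12 weeks of events after the endpoint and after the placebo switch. It cannot be determined for the preliminary Week 6 analysis, and it leaves unclear who counts as a completer.

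It would be too strong to say that the trial's primary result is affected. The MITT analysis, the step-down tests and the sample size do not use the PP set. The assumed 10% to 25% exclusion would raise the standard error by about 5% to 15%. Bias needs exit to be related to Week 6 Hb, which the documents neither establish nor rule out. The change is worth making because it is nearly free and removes the selection on later events.

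**What to change.** In Protocol 11.4.2 and SAP 4.4.2, replace the single PP definition with two.

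- **Week 6 PP set:** MITT subjects who completed the Week 6 visit with an observed Week 6 Hb, had at least 80% compliance from Day 1 to Week 6, and had no major deviation expected to affect the primary endpoint. Lock membership before the Week 6 unblinding and use it unchanged in the final analysis.
- **Later PP set:** for Week 16 and later summaries, require completion, data and compliance through Week 16. Staff who remain blinded should do the classification.

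The second set is needed because SAP 4.7.2.2 to 4.7.3 use PP beyond Week 6. A Week 6 rule alone would admit subjects who left or stopped complying afterwards.

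The cost is a short wording change in each document, two PP flags instead of one, and a classification step before the Week 6 unblinding. No new data are needed.

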4.4.3 Analysis Population for the PK Analysis

The PK summaries and analyses will be based on the **pharmacokinetics (PK) population**. The PK population is defined as all subjects in the safety population who have a pre-dose PK sample at Week 4. Subjects will be summarized and analyzed by actual treatment group.

4.5 Demographic and Other Baseline Characteristics

The demographic and other baseline characteristics will be summarized for the MITT and safety populations. The following summaries will be provided:

- A summary of demographic variables (e.g. age, gender, weight, height and body mass index [BMI]) by treatment group and all subjects.
- A summary of other relevant variables (e.g. etiology of CKD and smoking status) by treatment group and all subjects.
- A summary of relevant medical and surgical history by treatment group and all subjects.
- A summary of relevant medical history by treatment group and all subjects.
- A summary of prior and concomitant medications within 30 days prior to the first study drug dose up to and including Week 6 by treatment group and overall.
- For the final analysis, a summary of concomitant medications after Week 6 will be provided.

Age will be calculated as the number of complete years between a subject's birth date and the date of informed consent.

By-subject listings of demographic data and other baseline characteristics (as summarized above) will be provided.

4.6 Treatment Compliance

The treatment compliance will be summarized for the MITT and safety population. The following summary will be provided.

- A summary of the treatment compliance measures (i.e. $\geq 80\%$ compliance and $< 80\%$) by treatment group and study visit.

A by-subject listing of treatment compliance data will be provided.

4.7 Efficacy Evaluation

4.7.1 Analysis and Data Conventions

This study is designed to test for dose-response relationship. An analysis of covariance (ANCOVA) model will be used to compare absolute change from pre-treatment in Hb between the 3 vadadustat dosing groups and the placebo group. The model will include treatment assignment (3 dosed groups and one placebo group) and pre-treatment Hb value as a covariate. A step-down procedure will be used to control the overall type I error rate for the multiple comparisons. Testing of the highest dose compared with placebo will be conducted first. If and only if this comparison is significant, then testing will proceed to comparison of the next lower dose and placebo, and so on. Therefore, no multiplicity adjustment will be needed for this analysis.

A linear regression dose-response modeling will be performed as a secondary analysis.

$$Y = \beta_0 + \beta_{dose}X$$

where Y is change in Hb and X is vadadustat dose. β_x s are parameters of the model. β_0 is intercept and β_{dose} is slope, respectively.

The null hypothesis for the dose response will be that the regression coefficient of slope parameter is zero. The alternative hypothesis will be that the regression coefficient is not zero. Symbolically, this is expressed as follows:

$$\begin{aligned} H_0: \beta_{dose} &= 0 \\ H_1: \beta_{dose} &\neq 0 \end{aligned}$$

This hypothesis will be tested using a 0.05 two-sided significance level.

4.7.1.1 Multi-center Studies

Not Applicable. Analysis of center effect is not planned.

4.7.1.2 Adjustments for Covariates

The primary efficacy analysis will be adjusted for the pre-treatment measure of primary efficacy variable.

An ‘unadjusted’ sensitivity analysis will be performed to assess the robustness of the study conclusion.

4.7.1.3 Handling of Missing Data

For the MITT population analyses for the primary efficacy variable, the Last Observation Carried Forward (LOCF) approach will be used to impute missing data for primary efficacy analysis.

Subjects who underwent dose reduction before week 6 will not be analyzed differently from subjects who did not undergo dose reduction. This means we will use the actual Hb at week 6 for all subjects except the missing data, which will be carried from the last Hb before week 6 and after baseline.

- If a Baseline value is missing, the last value prior to baseline will be carried forward to the Baseline value but not to further values during the treatment period.
- For post-Baseline assessments, hemoglobin measurements at end of treatment and follow-up visits are not carried forward. Other than that, the most recent post-baseline assessments to the primary evaluation period (week 6) will be carried forward. Baseline and pre-Baseline values will not be carried forward to the post-Baseline visits.

For the secondary endpoint analyses, data will be used as observed and no imputation method will be used.

4.7.1.4 Multiple Comparisons/Multiplicity

Analysis of one primary variable [Change in Hb] and one time point of primary interest [Week 6 visit] has been defined for this study. Though 3 pairwise comparison between placebo and dosed group is planned, step-down procedure will be used to control the overall type I error rate. The secondary variables defined are intended to provide supportive evidence relating to the primary objective and no labeling claims are intended. Though one preliminary analysis is planned before the final analysis, primary analysis will not be changed. Therefore no adjustments for multiplicity are required.

4.7.1.5 Preliminary (6-Week) Analysis

After all subject performed assessment of the Week 6 Visit, preliminary analysis will be performed. As the study conduct and final analysis will not be modified by this analysis, no alpha adjustment is proposed. It is expected that this 6-week data will be identical for the preliminary analysis and the final analysis of the complete dataset. Any changes between the preliminary analysis and the final analysis will be documented. The preliminary analysis will be performed by the independent unblinded team. All data through the cutoff date of the last subject randomized who completes week 6 will be analyzed. Blinding of blinded team and investigators will be maintained to prevent potential bias.

4.7.1.6 Examination of Subgroups

Not Applicable. No subgroup analysis is planned.

4.7.2 Primary Efficacy Variable – Mean Change in Hb from Pre-treatment to the End of the Primary Efficacy Period (Week 6)

The primary variable for the assessment of efficacy is the change from pre-treatment to Week 6 in Hb (g/dL). Change in Hb is defined as the Hb measured at the Week 6 visit

minus the mean pre-treatment Hb. Pre-treatment Hb is defined as the average of 3 Hb values obtained prior to treatment based on 2 qualifying screening Hb values and the Hb value at the baseline visit (Day 1). If screening visit are not performed for some clinical consideration, pre-treatment HB will be calculated as average of available screening HB values and baseline visit without any screening visit imputation. e.g. if only one qualifying screening HB values available in the screening period, then Pre-treatment Hb is calculated as the average of 2 Hb values : only 1 qualifying screening Hb values and the Hb value at the baseline visit (Day 1).

For the primary analysis, the LOCF approach will be used to impute missing data.

4.7.2.1 Summary of actual value and change in Hb at week 6

The primary analysis population for efficacy will be MITT population. The following summary will be provided:

- A summary of actual value of Hb by treatment group at baseline and week 6. A summary of the change (absolute and percent) from pre-treatment average in Hb by treatment group at week 6. 1st and 3rd quartiles (Q1, Q3) as well as the mean, SD, median, minimum, maximum and number of observations will be shown. P values for overall comparison and treated groups vs. placebo on change from pre-treatment will also be presented.
- A waterfall plot for absolute Hb change from pre-treatment average for each treatment group at week 6.

The effect of treatment in terms of the change from pre-treatment to Week 6 in Hb will be analyzed using a one-way analysis of covariance (ANCOVA). The statistical model will assess the main effect of treatment, adjusted for pre-treatment average. Least-squares (LS) means for each treatment and their 95% confidence intervals (CIs) will be presented. Three post-hoc pairwise comparison, i.e., Placebo vs 150 mg, placebo vs 300 mg, and placebo vs 600 mg, will be done. Unadjusted one-way analysis of variance (ANOVA) will be performed for sensitivity.

The simple linear regression between the change from pre-treatment to Week 6 in Hb and dose will be calculated. The regression coefficients and their standard errors, p-values of test of regression parameters and their 95% CIs will be presented. The test of slope parameter will be used to evaluate dose response relationship.

As sensitivity analyses, efficacy endpoints will also be analyzed using the PP population.

A by-subject listing of actual values and change (absolute and percent) from baseline in Hb will be provided.

4.7.2.2 Summary of actual value and change in Hb from baseline to week 6 and beyond

The analysis population for efficacy will be MITT and PP population. The following summary will be provided:

- A summary of actual value of Hb by treatment group and study visits. 1st and 3rd quartiles (Q1, Q3) as well as the mean, SD, median, minimum, maximum and number of observations will be shown. Summary of pre-treatment average will also be presented.
- A summary of the change (absolute and percent) from baseline in Hb by treatment group and study visits.
- A plot showing the mean Hb value over time within each treatment group. 95% CI of these means will be shown as error bar and sample size in each group at each time point will be shown.
- Plots of individual profile of Hb values over time within each treatment group.
- Box plots of absolute Hb changes for each treatment group from pre-treatment study average to week 6.
- Box plots of absolute Hb changes for each treatment group from pre-treatment study average to week 16

A by-subject listing of actual values and change (absolute and percent) from baseline in Hb will be provided.

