4.7.3 Secondary Efficacy Variables

The analysis population for efficacy will be MITT and PP population.

Change from baseline visit to Week 6 in HB (g/dL).

The following summaries will be provided:

- A summary of actual value of Hb by treatment group at baseline and week 6. A summary of the change (absolute and percent) from baseline in Hb by treatment group at week 6. 1st and 3rd quartiles (Q1, Q3) as well as the mean, SD, median, minimum, maximum and number of observations will be shown. P values for overall comparison and treated groups vs. placebo on change from baseline will also be presented.
- The effect of treatment in terms of the change from pre-treatment to Week 6 in Hb will be analyzed using a one-way analysis of covariance (ANCOVA). The statistical model will assess the main effect of treatment, adjusted for Baseline. Least-squares (LS) means for each treatment and their 95% confidence intervals (CIs) will be

presented. Three post-hoc pairwise comparison, i.e., Placebo vs 150 mg, placebo vs 300 mg, and placebo vs 600 mg, will be done. Unadjusted one-way analysis of variance (ANOVA) will be performed for sensitivity.

- The simple linear regression between the change from Baseline to Week 6 in Hb and dose will be calculated. The regression coefficients and their standard errors, p-values of test of regression parameters and their 95% CIs will be presented. The test of slope parameter will be used to evaluate dose response relationship.
- A waterfall plot for absolute Hb change from baseline for each treatment group at week 6.
- A summary of the number and percentage of subjects who achieved a ≥ 1 g/dL increase in Hb from baseline average will be provided by treatment group.

Time to reach target Hb level

Time to reach target Hb level of 10.0-12.0 g/dL from baseline is defined for subjects with Hb <10.0 g/dL at the baseline visit as following:

First post-treatment assessment date with value of Hb ≥ 10.0 and ≤ 12.0 g/dL – the baseline visit date +1. If target Hb level is not achieved, last Hb assessment date will be used as censored date.

A summary of time to reach target Hb level will be provided for subjects with Hb <10.0 g/dL at the baseline visit by treatment group.

A by-subject listing will be provided.

Hb within target Range

A summary of the number and percentage of subjects within target Hb 10-12 g/dL at the end of the dose adjustment and maintenance period (Week 16) will be provided by treatment group.

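### The dose-response slope test leaves out pre-treatment Hb although the ANCOVA on the same response adjusts for it, and the change-from-baseline ANCOVA in SAP 4.7.3 names the wrong response

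*SAP*

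**What the plan says.** **Slope test.** SAP 4.7.1 gives the step-down ANCOVA with pre-treatment Hb as covariate, then states: "A linear regression dose-response modeling will be performed as a secondary analysis". The model has an intercept and a dose term only, "where Y is change in Hb and X is vadadustat dose". SAP 4.7.2.1 repeats this for the primary variable, "The simple linear regression between the change from pre-treatment to Week 6 in Hb and dose will be calculated", and gives it a role: "The test of slope parameter will be used to evaluate dose response relationship". The slope model in SAP 4.7.3 likewise contains dose only.

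**Covariate rule.** SAP 4.7.1.2 says "The primary efficacy analysis will be adjusted for the pre-treatment measure of primary efficacy variable" and provides an unadjusted analysis for sensitivity. In 4.7.2.1 this becomes ANCOVA with an unadjusted ANOVA beside it. No adjusted slope is planned anywhere.

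**Change-from-baseline block.** SAP 4.7.3 opens with Hb change from the baseline visit to Week 6. Its first bullet says "P values for overall comparison and treated groups vs. placebo on change from baseline will also be presented", and its regression and waterfall plot also use change from baseline. The ANCOVA bullet instead says "The effect of treatment in terms of the change from pre-treatment to Week 6 in Hb will be analyzed", and then "The statistical model will assess the main effect of treatment, adjusted for Baseline". SAP 4.2 defines pre-treatment Hb as the average of two screening values and the Day 1 value, so it is not the baseline-visit value.

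**The concern.** The primary objective is the dose-response relationship, and the slope is the plan's only model that treats dose as a continuous variable. It will be reported next to covariate-adjusted pairwise results on the same response. Where the two tell different stories, part of the difference may come from nothing more than one model using pre-treatment Hb and the other not. Precision may also be given away on the question the trial was set up to answer.

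In 4.7.3 the problem is one of specification. The table promises p-values for change from baseline, but the model that supplies them is written for another variable. A programmer must either guess the intent or produce LS means and p-values that do not belong to the table they appear in.

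**Working it through.** **1. The plan's own power figure.** Protocol 11.2 states more than 85% power for 600 mg against placebo (difference 1.35 g/dL, SD 0.9, 12 per group, 10% dropout, two-sided 0.05). With 12 × 0.9 = 10.8 per group, SE = 0.9 × √(2/10.8) = 0.387 and the noncentral t gives 91.2% (93.9% at 12 per group, 88.7% at 10). The stated bound is met. The plan gives no power for the slope test or for the 4.7.3 ANCOVA. SAP 4.10 uses SD 0.68 instead; the relative SE changes below do not depend on which SD is taken.

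**2. Unadjusted slope.** Assume a linear response reaching 1.35 g/dL at 600 mg. With dose in units of 600 mg the values are 0, 0.25, 0.5 and 1 (mean 0.4375), and the squared deviations sum to 0.1914 + 0.0352 + 0.0039 + 0.3164 = 0.5469.

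- Sxx = 10.8 × 0.5469 = 5.906
- SE = 0.9/√5.906 = 0.370 g/dL per 600 mg
- df = 43.2 − 2 = 41.2
- Power = 94.5%

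**3. Adjusted slope.** Let k = SD of pre-treatment Hb / SD of Week 6 Hb, and r = their correlation. Neither is in the documents; k from 0.5 to 1 and r from 0.3 to 0.7 are assumed. Then

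corr(change, pre-treatment) = (r − k)/√(1 + k² − 2rk),

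and adjustment multiplies the SE by √(1 − corr²), times √(1 + 1/df) for the estimated covariate effect. For example, k = 1 and r = 0.3 give corr = −0.7/√1.4 = −0.592, an SE factor of 0.806, and 0.816 after the covariate cost.

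| k | SE reduction before the df cost, r = 0.3 / 0.5 / 0.7 | Adjusted power, r = 0.3 / 0.5 / 0.7 |
|---|---|---|
| 1 | 19 / 13 / 8% | 99.2 / 98.2 / 96.8% |
| 0.75 | 10 / 4 / 0.2% | 97.3 / 95.5 / 94.1% |
| 0.5 | 2 / 0 / 4% | 94.8 / 94.0 / 95.4% |

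After the df cost the range runs from an 18% reduction to a 1% increase. The gain vanishes when k = r. The entry limit of mean screening Hb below 10.0 g/dL (Protocol 7.2) narrows the pre-treatment distribution and points to k below 1, the lower part of the range. Simulation with random 10% dropout agrees with these powers to within about 0.3 percentage points. In a separate simulation under the null hypothesis, type I error was about 0.048 for both models.

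**4. The 4.7.3 ANCOVA.** Write S for the mean of the two screening values, B for Day 1 and W for Week 6. Pre-treatment Hb is (2S + B)/3, so

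W − pre-treatment = (W − B) + (2/3)(B − S).

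With B as covariate, the written contrast equals the intended contrast minus two-thirds of the between-arm difference in S given B. Randomization makes that difference zero on average, but not in any one trial.

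Its size was simulated with 4000 trials per setting and 11 per arm. Between-subject SD 0.5, visit-to-visit SD 0.3 or 0.5, and response SD 0.7 are all assumed, with a linear effect of 1.35 g/dL at 600 mg.

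| Visit SD | Mean 600 mg contrast, written / intended | Mean absolute difference at 600 mg | Disagree on p<0.05, 600 mg | Disagree on p<0.05, 300 mg |
|---|---|---|---|---|
| 0.3 | 1.362 / 1.361 | 0.077 g/dL | 1.6% | 8.8% |
| 0.5 | 1.355 / 1.355 | 0.115 g/dL | 4.5% | 11.0% |

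**The case against.** On the slope, the strongest reply is that no rule is broken. The regression is labelled secondary, the covariate rule names the primary analysis only, and SAP 4.7.1, 4.7.2.1 and 4.7.3 agree with one another in describing a dose-only model. Validity is intact and power is already 94.5%. In two of the nine settings adjustment slightly lowers power (94.1% and 94.0%), and the entry limit makes the low-gain settings more plausible. The slope and the pairwise contrasts would also differ anyway, because the slope imposes linearity. All of that stands, and it keeps this part to a modest improvement. It does not explain why the plan's own pattern, adjusted first and unadjusted for sensitivity, stops short of the one model aimed at dose-response. The worst modelled cost is about 1% in SE.

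On 4.7.3, the reply is that the intended variable is clear from the surrounding bullets and from the amendment rationale in SAP 6.1.1, and that the contrasts are unbiased either way. The 300 mg disagreement also needs context. That contrast has only about 39-50% power in the simulated settings, and the correctly written 4.7.3 ANCOVA disagrees with the primary ANCOVA in about 9% of the same trials. Much of the disagreement is therefore inherent in using two baselines. This limits the consequence but leaves the contradiction in the operative text, and the primary step-down test is unaffected in either case.

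**Conclusion.** Both parts hold.

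The 4.7.3 ANCOVA response is wrong as written, and this follows from the text alone. Its numerical effect (a mean difference of 0.08 to 0.12 g/dL at 600 mg, and disagreement on significance in 2-5% of trials at 600 mg and 9-11% at 300 mg) rests on assumed variance components.

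The unadjusted slope is valid but inconsistent with the ANCOVA on the same response, and it may be less precise than it could be. Its size rests on a linear response, the Protocol's 1.35 g/dL, SD 0.9 and 10% dropout, and the assumed ranges of k and r. Because k is probably below 1, the likely gain is small; consistency with the primary model is gained in every case. The changes should be made, but neither point threatens the primary analysis.

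**What to change.** - **SAP 4.7.1 and 4.7.2.1:** add pre-treatment Hb to the slope model, Y = b0 + b1 × dose + b2 × pre-treatment Hb, and test b1. Keep the simple regression as the unadjusted sensitivity analysis, mirroring ANCOVA and ANOVA.
- **SAP 4.7.3, regression:** add Day 1 Hb in the same way, again with the simple regression for sensitivity.
- **SAP 4.7.3, ANCOVA:** set the response to change from the baseline visit to Week 6, with Day 1 Hb as covariate.

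The cost is one error degree of freedom of about 41 in each slope model, one model term and one corrected phrase. No new data are needed. The changes should be settled before the unblinded Week 6 analysis described in SAP 4.7.1.5.
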